## **Eligibility criteria**

### **Inclusion criteria**

- Adults ( $\geq 18$  years)
- Presentation compatible with hyperacute stroke syndrome
- One or more of the following symptoms present at time of enrolment: Dysphasia, neglect (NIHSS 1-2), hemianopia (NIHSS 1-3), or limb weakness (NIHSS on affected arm and/or leg 1-4)
- Treatment can be commenced between 3 and 5 hours from onset of symptoms (for patients with wake-up stroke, treatment no more than 5 hours after patient awakens)
- Systolic BP  $\geq 120$  mmHg
- If a CT/MR scan has already been performed, then it shows acute intracerebral haemorrhage or ischaemic stroke, or is normal. (If a CT scan has not been performed then it should be performed as soon as possible after treatment)
- For participants who lack capacity to consent for themselves and have no relative/friend available: Waiver of consent for treatment to ensure GTN given in 3-5-hour time-window (and thrombolysis not delayed if ischaemic stroke)

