Eligibility criteria	
Inclusion:  120 adults (≥18 years) with presentation compatible with stroke  Treatment 3-5 hours post ictus (for patients with wake-up stroke, treatment no more than 5 hours after patient awakens)  One or more of the following symptoms present at time of enrolment:  Dysphasia, neglect (NIHSS 1-2), hemianopia (NIHSS 1-3), or limb weakness (NIHSS on affected arm and/or leg 1-4)  Systolic BP (≥120 mmHg)  If a CT/MR scan has already been performed, then it shows acute intracerebral haemorrhage or ischaemic stroke, or is normal.  Waiver of consent for treatment to ensure GTN given in 3-5-hour time-window (and thrombolysis not delayed if ischaemic stroke).
 
Exclusion:  mRS ≥4  Glucose (BM stix or equivalent) <3 mmol/l  Glasgow coma scale ≤8  Witnessed seizure at presentation  Known life expectancy <6 months.  Patient presenting with sensory symptoms only  Known stroke mimic, aneurysmal subarachnoid haemorrhage, or haemorrhage due to venous thrombosis  Systolic blood pressure <120 mmHg  Known allergy to glyceryl trinitrate (Transiderm-Nitro) patch  Known sensitivity to Duoderm hydrocolloid dressing  Planned for palliative care only  Recent use of phosphodiesterase type 5 (PDE5) inhibitors, e.g., sildenafil (Viagra®)  If a CT/MR scan has already been performed, then it shows a non-stroke lesion that explains the acute presentation  Known previous enrolment in ENOS-2

Description of interventions	
Active: Transdermal glyceryl trinitrate (GTN) 5 mg placed on back or shoulders and applied for 2 days  Comparator: Transdermal Duoderm hydrocolloid dressing placed on back or shoulders and applied for 2 days.

Duration of study	
The trial will last 36 months (until May 2024), with recruitment occurring over 31 months (until February 2024). Once enrolled, participants will be treated for 2 days, and followed-up at 90 (primary outcome).

Randomisation and blinding	
Patients will be randomised (1:1) to receive either glyceryl trinitrate patches or sham patches. Randomisation will be performed by the Nottingham Stroke Trials Unit (STU) and involve computerised stratification by stroke type (IS or not known; ICH) and minimisation on age, severity, time, systolic blood pressure and candidate for or received reperfusion therapy. Patients, relatives, researchers and outcome assessors will be masked to treatment allocation.

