- GTN is safe in patients with severe carotid stenosis.

Further, the effect of GTN on functional outcome appears to be time-dependent when administered after stroke:

[figure not shown]
- <2.0 hours: No effect; indeed, GTN may cause harm in ICH in this ultra-acute period (interpretation from RIGHT-2 )
- 2.5 to 5.5 hours: May improve functional outcome (interpretation from ENOS-early  and meta-analysis, Figures 1 , 2).
- >6 hours: No effect (interpretation from GTN 1/2/3 and ENOS and an individual patient data meta-analysis ).

(The positive effect of GTN on functional outcome in the phase II RIGHT trial is ignored here because it was small.)

**Figure 1. Meta-analysis of GTN versus no GTN on end of trial functional outcome in patients treated within 6 hours of stroke onset (from )**

**Figure 2. Meta-analysis of GTN versus no GTN on end of trial death in patients treated within 6 hours of stroke onset (from )**

In summary, GTN has been associated with beneficial effects on function and other clinical outcomes in hospitalised patients treated up to 6 hours after ictus. However, benefit was not seen in patients treated prior to hospital admission and there was weak evidence that ultra-acute treatment within 2 hours was associated with harm. As a result, ENOS-2 will assess, in a novel design, the feasibility of recruiting patients between 3 and 5 hours after ictus; if feasible, a larger safety and efficacy trial will be performed in this group of patients.

ENOS-2 will assess the feasibility, safety, and efficacy of hospital-delivered GTN when administered hyper-acutely after stroke. Five of the six GTN trials had a lower limit for systolic blood pressure of  $\geq 100$  mmHg,  $>120$  mmHg or  $\geq 140$  mmHg, the first study had no lower limit. Since several potential mechanisms by which GTN might work are BP-independent, ENOS-2 will follow the RIGHT-2 protocol and include patients with high-normal BP as well as high BP, with a lower limit set to  $\geq 120$  mmHg. This has the advantage that the results will apply to a wider population of stroke patients and include more patients with severe stroke (some of whom have SBP  $<140$  mmHg).

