#### **Primary endpoint**

The primary end point of the study is the feasibility of recruiting and treating 120 patients (100 IS, 20 ICH) between 3 and 5 hours after stroke.

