## Informed consent

Stroke, including ischaemic stroke and intracerebral haemorrhage, is a medical emergency with limited treatment options. Further, rapid deterioration can occur early, leading to brain damage, long term disability or death. Stroke can cause significant brain injury and many patients may not be physically or mentally capable of giving informed consent to participate in a clinical trial. There is evidence from previous trials in stroke (involving >4000 patients in ENOS and three hospital pilot trials) that transdermal GTN (5 mg) is safe if given after 2.5 hours. The need for urgent treatment, in an attempt to improve outcome and reduce deterioration, means that it would be inappropriate to delay treatment until fully informed consent can be obtained from an incapacitated patient. Further, patients with IS should be considered for intravenous thrombolysis and this must take precedence over any trial that requires consent for treatment.

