### **26 Subgroup analyses:**

The primary clinical outcome will be analysed in subgroups consisting of the minimisation factors:

- Age (years):  $\leq 70$ ,  $> 70$
- Stroke severity, NIHSS (/42):  $\leq 10$ ,  $> 10$
- Time after stroke (minutes):  $\leq 220$ ,  $> 220$
- Systolic blood pressure (mmHg):  $\leq 160$ ,  $> 160$
- Received reperfusion therapy: yes, no

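### Wake-up strokes are timed only by an upper limit from awakening, yet every recruit counts towards an endpoint defined as treatment 3 to 5 hours after stroke

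*Protocol*

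**What the plan says.** For most patients the window has two limits and one clock: "Treatment can be commenced between 3 and 5 hours from onset of symptoms" (Protocol, Inclusion criteria). For wake-up stroke the same bullet adds a bracket: "for patients with wake-up stroke, treatment no more than 5 hours after patient awakens". The Protocol Synopsis and SAP section 20a carry the same exception. No section of either document defines onset for wake-up stroke or states a lower limit for it.

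The endpoint and design statements have no such exception. The primary endpoint in the Protocol, repeated in SAP 24a, is "the feasibility of recruiting and treating 120 patients (100 IS, 20 ICH) between 3 and 5 hours after stroke". Trial Configuration in the Protocol and SAP section 8 give the same 3 to 5 hours, the first for initial treatment and the second for randomisation.

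Counting is by recruitment. SAP Table 2 shows recruits out of 120, split by stroke type, with no line for treatment inside the window. The progression figure is 70 recruits in the Protocol Synopsis, SAP 25b and SAP Table 2, and 75 in the Protocol sections on statistical methods and sample size.

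Time is a minimisation factor, a covariate (SAP 25d and the caption of SAP Table 3) and a subgroup factor cut at 220 minutes (SAP 26, "Time after stroke (minutes"). Wake-up stroke appears in the SAP analysis tables only as a baseline row in Table 1.

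**The concern.** The trial asks whether a narrow window can be met. If some recruits were admitted under a different timing rule, the headline count does not answer that question, and the planned tables do not separate the two groups.

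The Protocol's own background makes the boundaries matter. It reads earlier GTN data as showing no effect before 2 hours, where "GTN may cause harm in ICH in this ultra-acute period", possible benefit from 2.5 to 5.5 hours, and no effect beyond 6 hours. Timing from awakening can admit patients from the late band. If the minimum is taken not to apply, it can also admit some from the early band. The inclusion criteria allow the CT scan to follow treatment, so haemorrhage may not yet be known when the first patch goes on. Rapid or waived consent rests partly on safety more than 2 hours after onset (Protocol, Recruitment) and on evidence that "transdermal GTN (5 mg) is safe if given after 2.5 hours" (Protocol, Informed consent). Both statements presuppose a known time from onset.

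The analysis has a parallel gap. A variable labelled as time from onset to randomisation has no stated value for someone whose onset was not observed.

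**Working it through.** **1. The plan's own figure.** The Protocol section on Recruitment puts the window at 2 hours. From the limits, 5 − 3 = 2 hours, so this reproduces.

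**2. What the bracket allows.** Let G be the time from onset to awakening (unknown, between 0 and the length of sleep L), and A the time from awakening to treatment. Time from onset to treatment is T = G + A. The bracket states only A ≤ 5.

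- Reading (a), minimum does not apply: 0 < A ≤ 5, so T runs from just above 0 to L + 5.
- Reading (b), minimum kept and timed from awakening: 3 ≤ A ≤ 5, so T runs from 3 to L + 5.
- Reading (c), minimum kept and timed from onset: T ≥ 3 and A ≤ 5, so T again runs from 3 to L + 5.

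With 6 hours of sleep the upper end is 11 hours, and with 8 hours it is 13. If the 5-hour limit from onset also still applied, T ≤ 5 would already imply A ≤ 5 and the bracket would do nothing. On every reading that gives the bracket an effect, T can exceed 5 hours. Only reading (a) allows T below 3 hours.

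**3. Illustrative shares among wake-up patients.** These assumptions are mine; the documents give no distribution. Take onset uniform over L hours of sleep.

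Reading (a), A uniform on 0 to 5: the share under 3 hours is 4.5/(5L). The share over 5 hours is L/10 for L = 4 and 1 − 12.5/(5L) for L of 6 or more. Reading (b), A uniform on 3 to 5: the share over 5 hours is 1 − 1/L.

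| L (hours) | (a) under 3 h | (a) 3 to 5 h | (a) over 5 h | (b) over 5 h |
|---|---|---|---|---|
| 4 | 22.5% | 37.5% | 40.0% | 75.0% |
| 6 | 15.0% | 26.7% | 58.3% | 83.3% |
| 8 | 11.25% | 20.0% | 68.75% | 87.5% |
| 10 | 9.0% | 16.0% | 75.0% | 90.0% |

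If onset always falls in the last hour of sleep (mean G = 0.5), reading (a) gives (3 − 0.5)/5 = 50% under 3 hours, 0.5/5 = 10% over 5 hours and 40% inside. Reading (b) gives 0.5/2 = 25% over 5 hours. A simulation of 1,000,000 draws agrees with all these figures to within 0.2 percentage points.

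Starting A at zero leaves no time for travel and assessment. With A uniform on 1 to 5 and onset uniform over sleep, the share under 3 hours is 0.5/L, which is 12.5% at L = 4 and 5.0% at L = 10.

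**4. Effect on the count.** With wake-up share w (assumed 5% to 25%), known-onset recruits number N(1 − w).

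| N recruited | w = 5% | w = 25% |
|---|---|---|
| 120 | 114 | 90 |
| 75 | 71.25 | 56.25 |
| 70 | 66.5 | 52.5 |

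At 75 recruits the known-onset count falls below 70 once w exceeds 5/75 = 6.7%.

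**5. The time variable.** SAP Table 1 marks onset to randomisation as a minimisation variable, SAP 25d and Table 3 adjust for it, and SAP 26 splits it at 220 minutes. None says what is entered for a wake-up patient. If awakening time is entered, two origins are pooled. If onset is left blank, SAP 27 (no imputation) would drop these patients from adjusted models. The documents do not say which applies.

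**The case against.** The strongest reply is that the bracket is silent about the minimum rather than removing it. It sits inside a sentence that states 3 to 5 hours, and the design statements repeat that window. This stands: a reader might infer that the 3-hour limit is dropped and that someone treated within an hour of waking is plainly eligible, but the text supports that only on reading (a). The reply does not reach the upper limit, which fails on all three readings.

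A reader might also infer that the safety statements behind rapid consent fail for all wake-up patients. They do not. A patient who woke 4 hours ago is at least 4 hours from onset and so past both stated thresholds; for late-treated patients the background's message is lack of effect. Only patients treated soon after waking could fall outside those statements, and only on reading (a) with recent onset.

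Nor do the documents show that the time variable runs from awakening. The case report form is not among them and may capture when the patient was last known well. The supportable statement is that the origin is undefined.

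Three further points have weight. The progression figures are not hard gates: the Protocol allows progression after lower recruitment. If the definitive trial kept the same eligibility rule, all recruits would be the right basis for projecting its accrual, so the total must still be reported. Comparisons of mRS are exploratory, so dilution of an efficacy signal matters little here. SAP Table 1 also already gives wake-up stroke by arm and a median and range for onset to randomisation. That lets a reader subtract wake-up patients from the total, but not count the known-onset patients first treated at 3 to 5 hours.

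**Conclusion.** The point holds in limited form. The eligibility rule for wake-up stroke and the primary endpoint use different time origins, and the minimum for wake-up stroke is unstated. As written, the feasibility result would include patients not shown to have been treated 3 to 5 hours after stroke. That they count at all follows from the lack of any exclusion and from the layout of SAP Table 2; no sentence says so directly.

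The size depends on a wake-up share that neither document gives. At 5% to 25%, the gap between total and known-onset recruits is about 4 to 19 at 75 recruited and 4 to 18 at 70. That could change how the result reads against either progression figure, although neither is binding. A reader might infer that a 10% to 25% share means 12 to 30 of 120 participants lie outside the window. That is a ceiling on an assumed share: under reading (a) with onset uniform over sleep, 16% to 38% of wake-up patients still fall inside it.

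The undefined time origin for minimisation, adjustment and the subgroup needs no assumption.

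**What to change.** - **Reconcile the passages.** Bring the wake-up clause (Protocol Synopsis and Inclusion criteria, SAP 20a) into line with the endpoint and design statements (Protocol Trial Configuration and Primary endpoint, SAP 8 and 24a), and with the background time bands and the consent-related safety statements. State whether a minimum applies to wake-up stroke and from which time. Which clinical window is right is for the sponsor and investigators; this review takes no view.
- **Record both times.** Capture last-known-well and awakening times for every wake-up participant, if the case report form does not already do so.
- **SAP 24a, 25b and Table 2.** Report total recruited, then on separate lines known-onset participants first treated at 3 to 5 hours, and wake-up participants. Rest any statement about feasibility 3 to 5 hours after stroke on the known-onset line.
- **SAP 25d and 26.** State the time origin used for wake-up participants, including at minimisation. Add a wake-up indicator to the adjusted models, and leave these participants out of the 220-minute subgroup.

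The cost is one clarified criterion, at most one or two time fields and some SAP wording; the wake-up flag is already in SAP Table 1. The downside is that the known-onset count may be lower than the total.

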### **Exclusion criteria**

- mRS  $\geq 4$
- Hypotension or shock (systolic  $< 120$  mmHg)
- BP Glucose (BM stix or equivalent)  $< 3$  mmol/l
- Glasgow coma scale  $\leq 8$
- Witnessed seizure at presentation
- Known life expectancy  $< 6$  months
- Patient presenting with sensory symptoms only
- Known stroke mimic, aneurysmal subarachnoid haemorrhage, or haemorrhage due to venous thrombosis
- Known allergy to glyceryl trinitrate (Transiderm-Nitro) patch
- Known sensitivity to Duoderm hydrocolloid dressing
- Planned for palliative care only
- Recent use of phosphodiesterase type 5 (PDE5) inhibitors, e.g., sildenafil (Viagra®)
- If a CT/MR scan has already been performed, then it shows a non-stroke lesion that explains the acute presentation
- Known previous enrolment in ENOS-2

## Expected duration of participant participation

Study participants will be participating in the study for 90 days.

## Removal of participants from therapy or assessments

Participation in the trial is voluntary and patients are free to stop treatment, miss follow-up visits or withdraw completely from the trial at any stage without giving a reason.

- **Study medication:** This may be stopped at any time by the investigators or any treating clinician if deemed in the patient's best interest. Treatment (with GTN/sham) will be given on top of 'best medical care'. Stopping study medication does not constitute withdrawal and follow-ups should be continued as per this protocol.
- **Follow-ups:** These may be missed but this does not constitute withdrawal from the trial and the remaining follow-up visits should be continued as per this protocol.
- **Withdrawal from trial:** Participants may be withdrawn from the trial either at their own request or at the discretion of the Investigator. The participants will be made aware that this will not affect their future care. Participants will be made aware (via the information sheet and consent form) that should they withdraw the data collected to date cannot be erased and may still be used in the final analysis.

## Informed consent

Stroke, including ischaemic stroke and intracerebral haemorrhage, is a medical emergency with limited treatment options. Further, rapid deterioration can occur early, leading to brain damage, long term disability or death. Stroke can cause significant brain injury and many patients may not be physically or mentally capable of giving informed consent to participate in a clinical trial. There is evidence from previous trials in stroke (involving >4000 patients in ENOS and three hospital pilot trials) that transdermal GTN (5 mg) is safe if given after 2.5 hours. The need for urgent treatment, in an attempt to improve outcome and reduce deterioration, means that it would be inappropriate to delay treatment until fully informed consent can be obtained from an incapacitated patient. Further, patients with IS should be considered for intravenous thrombolysis and this must take precedence over any trial that requires consent for treatment.

### **Patient able to provide consent**

All participants who have capacity will provide verbal consent followed by written informed consent. The Consent Form will be signed and dated by the participant after treatment and before follow-up. The Investigator (or nominee) will explain the details of the trial and provide a Pictorial Information Sheet. The Pictorial Information Sheet has been specifically designed in order to speed up the process in this emergency condition. This approach has been successfully used in TICH-2 (Ref: ISRCTN93732214) and RIGHT-2 study (Ref: ISRCTN26986053) and is supported by stroke survivors (including those in the Nottingham Stroke Research Partnership Group). The Investigator will answer any questions that the participant has concerning study participation and follow-up. If requested, a more detailed information sheet will be provided. Participants will be given as long as they need to consider whether to consent to follow up.

If the participant is unable to write (e.g., in the presence of dominant hand weakness, ataxia or dyspraxia), witnessed verbal consent (or any mark made by the participant as intent to sign) may be recorded on the consent form by someone unconnected with the study.

Participants may discontinue treatment either at their own request or if it is felt in their best interest by the attending physician (for whatever reason); these participants remain in the trial and should have follow-up performed as per protocol. Participants may decline to have a follow up visit but should remain in the trial unless they specifically ask to be withdrawn. Participants may withdraw from the trial either at their own request (if they regain capacity) or at the request Investigator. Participants who withdraw from the trial will be informed that data already collected prior to withdrawal cannot be deleted and may still be used in final analyses

### ***Consent for treatment where participants lack capacity***

Participants who lack capacity but have a relative/friend present will be asked to provide verbal consent followed by written consent or proxy written consent after treatment for hospital and community-based follow-up. Ability to give consent will be determined by the participant's attending stroke physician or investigator as previously described:

- **Proxy consent.** Participants who regain capacity will be approached to give consent for further follow up, or to withdraw from the trial. Participants who die after treatment and before consent will have their data used without proxy consent since this avoids unnecessary stress to grieving relatives.

### ***Patient unable to give consent for follow-up (after treatment and before going home?)***

If the potential participant is unable to give meaningful consent (e.g., in cases of dysphasia, confusion, or reduced conscious level), a relative or close friend able to represent the patient's views and wishes will be approached with the pictorial information about the trial; this approach was used in RIGHT-2 (Ref: ISRCTN26986053). If requested, a more detailed information sheet will be provided. The Consent Form will be signed and dated by the legal personal nominee before the patient enters the trial. If the relative objects to the inclusion of the patient in the trial, their views will be respected, and the patient will not be enrolled.

If relatives are not physically present but are available and happy to speak on the telephone, the same procedure will be followed with the exception that the paper consent form will be countersigned by a witness unconnected with the study and signed by the relative upon their arrival to the hospital site. If the relative is unhappy to speak on the telephone or unable to decide, the patient will not be followed-up.

If the participant recovers capacity, their decision to continue or withdraw will overrule the decision of the nominee.

